7.5.2.4 Late Vaccine Reactions

All TEAEs will be reviewed by the Sponsor medical before databased hard lock to determined the terms for late vaccine reactions.

The number and percentage of subjects with each NCI- CTCAE v4.03 severity grade will be presented by treatment group.

7.5.3 Clinical Laboratory Evaluation

The baseline value for clinical laboratory evaluations is the last measurement taken prior to or on the day of the first injection of study drug.

Quantitative clinical laboratory variables, i.e. hematology, biochemistry, urine protein, urine creatinine and calculated ratio of protein/creatinine will be summarized descriptively (n, mean, standard deviation, minimum, median, and maximum) by visit. Clinical laboratory samples are drawn at screening, before each study drug injection, at each follow-up point for the injections, and at the last study visit (See Analysis visit window in Section 7.9.3).

Additionally, a within subject change will be calculated as the post-baseline measurement minus the baseline measurement and summarized descriptely.

7.5.3.1 Liver function Tests

Patients' liver safety evaluations will be summarized by the following categories:

- ALT or AST > 3xULN, > 5xULN, > 10xULN, >20xULN
- ALT > 3xULN, > 5xULN, > 10xULN, >20xULN
- AST > 3xULN, > 5xULN, > 10xULN, >20xULN

- ALP > 1.5xULN, >3xULN
- Total Bilirubin >2xULN
- ALT or AST > 3xULN **and** Total Bilirubin > 1.5xULN
- ALT or AST > 3xULN **and** Total Bilirubin > 2xULN
- ALT or AST > 3xULN **and** ALP < 2xULN **and** Total Bilirubin > 2xULN

The post-baseline values that are collected through day 380 and meeting the above criteria will be included without regards to the baseline values.

7.5.4 Vital Signs

The baseline value for vital signs is the last measurement taken on or prior to the first injection of study drug.

Vital signs (temperature, systolic blood pressure, diastolic blood pressure, respiratory rate, pulse rate,) and the change from baseline will be summarized using mean, standard deviation, minimum, median, and maximum by analysis visit (see Section [7.9.3](#)).

7.5.5 Pregnancies

Data will be listed.

7.5.6 Physical Examination

Data will be listed.

7.6 Analysis of PK

Not applicable.

7.7 Analysis of PD

Not applicable.

7.8 Interim Analysis (and Early Discontinuation of the Clinical Study)

No interim analysis evaluating the efficacy results are planned. The safety data will be monitored by the DMC according to the DMC Charter. Futility analyses with first 50 subjects and with 90 subjects were conducted ([Appendix 2](#)). The details will be described in the clinical study report.

At each futility analysis, Bayesian predictive probability of success (*BPP*) that the overall results of the trial will achieve the desired outcome, i.e., viremia rate on ASP0113 is at least 25% less than that on placebo, will be calculated based on the accrued data. If $BPP \leq 0.20$, then we conclude ASP0113 meets futility criterion.

The 20% cut-off for BPP is determined by simulation studies. The simulation studies cover the following scenarios: for each placebo viremia rate of 0.40, 0.46, and 0.51 the reduction in viremia due to ASP0113 run from 0% (no effect), 10% (marginal reduction), 25% (meaningful reduction), and 45% (significant reduction). Under each scenario, BPP is calculated at each interim look. The 20% cutoff produces satisfactory overall operating

characteristics of stopping the study early when there is little effect and preserving the power when ASP0113 shows the hypothesized effect.

A Data Monitoring Committee (DMC), external from the Sponsor, will be established to review safety and efficacy data at each interim look. A detailed description of the DMC, its role in this clinical trial, and the timing of the scheduled reviews will be provided in the DMC Charter.

Production of tables and listings will be performed by the independent statistician at Astellas / independent Data Analysis programmer at [REDACTED]. No member of the clinical trial team will have access to the reporting data base or will review the final tables and listings created for the DMC.

The primary responsibility of the DMC will be to monitor the trial for safety and futility concerns. The DMC will not stop the trial based on efficacy advantages. Therefore, the significance level need not be adjusted for the interim looks.

7.9 Handling of Missing Data, Outliers, Visit Windows, and Other Information

7.9.1 Missing Data

In the analysis of the primary endpoint, subjects who are lost to follow-up will be imputed as having viremia. Otherwise, viremia will not be imputed. Only observed viral loads from central labs meeting the definition of viremia will be counted.

Time to event variables will be considered censored at the time of the last assessment. Time to the first protocol-defined CMV viremia will be considered censored at the time of the last recorded central laboratory CMV measurement.

The start and stop dates of AEs and concomitant medication will be imputed to allocate the concomitant medication and AEs to a treatment group, in addition to determining whether an AE is/is not treatment emergent. Listings of the AEs and concomitant medications will present the actual partial dates; imputed dates will not be shown.

In case of missing partial start and stop dates for concomitant medications, the following rules will be used:

If start date is missing or partial:

- if month is missing, use January
- if day is missing, use the first day of the month under consideration
- if year is missing, use year of the informed consent date
- if entire date is missing, use informed consent date

If stop date is missing or partial:

- if month is missing, use December
- if day is missing, use the last day of the month under consideration
- if year or the entire date is missing, set to December 31st, 2099

If the imputed start date is after the stop date, then the imputed start date will be one day prior to the stop date.

For AEs, a missing or incomplete onset date will be imputed according to the following conventions for the purpose of defining TEAE.

- 1) Missing year, the AE will be count as TEAE
- 2) Missing month, the AE will be counted as TEAE if the year is equal to the consent year or one year later.
- 3) Missing date, using the last date of the month to determine TEAE.

No imputation of missing data for other variables will be done.

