5.4.2 Adverse Events

See Section 5.5 Adverse Events and Other Safety Aspects for information regarding adverse event collection and data handling.

All adverse events (AEs) and serious adverse events (SAEs) will be collected from signing of the informed consent through one year post Study Drug injection. AEs from the time of signing of informed consent through first dose of Study Drug should be captured on the medical history eCRF. If the AE is deemed possibly or probably related to Study Procedures prior to the first Study Drug injection, it will be recorded on the AE eCRF page. SAEs that occur from the signing of the informed consent form will be reported as per Section 5.5 and captured on the AE eCRF page. AEs and SAEs after the first dose of Study Drug should be captured on the AE eCRF page.

Data to be recorded includes the adverse event, date of onset, date of resolution, intensity, action taken with respect to Study Drug, treatment required, relationship to Study Drug and outcome of the event.

Adverse events ongoing at V13 will be followed up for as long as necessary to adequately evaluate the subject's safety or until the event stabilizes. If the event resolves during the study, a resolution date will be documented on the case report form.

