7 STATISTICAL METHODOLOGY

7.1 General Considerations

All statistical analyses and summary information will be generated according to this analysis plan and any deviations from this plan will be documented in the clinical study report. Any numerical rounding should be performed at the end of calculations. The p-values will be displayed with 3 decimal places. Statistical significance will be determined prior to rounding the p-value.

For continuous variables, descriptive statistics will include the number of subjects (n), mean, standard deviation, median, minimum and maximum. Frequencies and percentages will be displayed for categorical data. Percentages by categories will be based on the number of subjects with no missing data thus the percentages will add up to 100%. Baseline will be the last non-missing value on or prior to first study drug unless otherwise specified.

All efficacy comparisons will be tested at the 1-sided 0.05 significance level. Confidence intervals for efficacy estimates, if provided, will be constructed at 2-sided 90% level.

All data processing, summarization, and analyses will be performed using SAS® Version 9.1.3 or higher on Unix.

This SAP includes the data analysis for the primary study period (ie, 1-year post first study drug injection) which is defined as data collected through day 380 (=365+14+1 day). Certain data summary will consider analysis window as specified in each section. The long-term follow-up period is not covered by this SAP and will be managed in a separate SAP.

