7.5.1 Treatment Emergent Adverse Events

The coding dictionary for this study will be MedDRA Version 16.

TEAE is defined as an adverse event observed after the first study drug injection (Day 1) through Day 380. If the adverse event occurs on Day 1 and the onset check box is marked “Onset after first dose of study drug” or the onset check box is left blank, then the adverse event will be considered treatment emergent. If the adverse event occurs on Day 1 and the onset check box is marked “Onset before first dose of study drug”, then the adverse event will not be considered treatment emergent. If a subject experiences an event before the first study drug injection and continues during the primary study period, the event will be considered as TEAE only if it has worsened in severity during the primary study period (i.e., it is reported with a new start date).

An overview summary table will include the following:

- Number and percentage of subjects with TEAEs,
- Number and percentage of subjects with drug related TEAEs,
- Number and percentage of subjects with serious TEAEs,
- Number and percentage of subjects with serious drug related TEAEs,
- Number and percentage of subjects with TEAEs leading to permanent discontinuation of study drug injection, and
- Number and percentage of subjects with drug related TEAEs leading to permanent discontinuation of study drug injection, and
- Number of deaths.

The number and percentage of subjects with TEAEs, as classified by SOC and PT will be summarized for each treatment group. Summaries will be provided for:

- TEAEs
- drug related TEAEs,
- serious TEAEs,
- drug related serious TEAEs,
- TEAEs leading to permanent discontinuation of study drug,
- drug related TEAEs leading to permanent discontinuation of study drug,
- TEAEs excluding serious adverse events that equal to or exceed a threshold of 5.0% in any treatment group, and
- common TEAEs that equal to or exceed a threshold of 5.0% in any treatment group.

Drug-related AE is defined as any AE with at least possible relationship to study treatment as assessed by the investigator or with missing assessment of the causal relationship. AEs will be graded using National Cancer Institute (NCI)-Common Terminology Criteria for Adverse

Event (CTCAE) guidelines version 4.03. There are five grades: 1=mild, 2=moderate, 3=severe, 4=life threatening, 5=death. Missing severity will not be imputed.

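### The partial-date rules for adverse events contradict the treatment-emergent window at its late end, and contain no explicit stop-date check at its early end

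*SAP*

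**What the plan says.** SAP 7.5.1 sets the window: "TEAE is defined as an adverse event observed after the first study drug injection (Day 1) through Day 380". SAP 7.1 gives the same end day for the primary study period.

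SAP 7.9.1 then gives three rules for incomplete onset dates of adverse events:

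- Rule 1, year missing: "Missing year, the AE will be count as TEAE".
- Rule 2, month missing: "Missing month, the AE will be counted as TEAE if the year is equal to the consent year or one year later".
- Rule 3, day missing: "Missing date, using the last date of the month to determine TEAE".

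None of the three refers to the event's stop date. SAP 7.9.1 does contain a check of start against stop ("If the imputed start date is after the stop date, then the imputed start date will be one day prior to the stop date"), but it closes the block on concomitant medications, before the adverse-event rules begin.

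Protocol 5.4.2 determines which pre-dose events these rules can act on: "SAEs that occur from the signing of the informed consent form will be reported as per Section 5.5", and they go on the adverse-event page. So do pre-dose events judged related to study procedures. Other pre-dose events go to medical history.

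**The concern.** Moving an uncertain date to the end of its month is cautious near the first injection, because it tends to bring a doubtful event into the window. Near Day 380 the same move pushes events out. Rule 2 has a related fault: it is anchored on the consent year, while the window is anchored on the first injection, up to 47 days later. Both late-end errors remove true post-vaccination events from the TEAE tables, which is the non-conservative direction for the safety objective.

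At the early end, a serious event known to have ended before the first injection could be pulled into the window because nothing tells the programmer to look at its stop date. Such an event cannot be due to the vaccine.

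**Working it through.** **Inputs.** Window Day 1 to Day 380 (SAP 7.5.1). Consent from transplant Day -14, first dose at transplant Day 30 ± 3, Visit 13 at transplant Day 395 to 409 (Protocol Table 1 and footnotes). Routine adverse-event collection ends at Visit 13 (Protocol Table 1, footnote 13).

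**The plan's own figure.** 365 + 14 + 1 = 380, as SAP 7.1 states. Calendar date of Day 380 = first-dose date + 379 days.

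**Missing day, late end.** Suppose transplant is on 1 January 2014 and the first dose on 31 January 2014. Day 380 is 14 February 2015, and the latest allowed Visit 13 (transplant Day 409) is also 14 February 2015. An event dated February 2015 is set to 28 February, which is Day 394, and is not counted, although any onset collected by Visit 13 lies in the window. In general:

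- The error arises unless Day 380 is a month end. Over all first-dose dates in 2014 and 2015 it arises for 96.7%.
- On average 14.7 in-window days per subject lie in the affected month, so a simple ceiling is 14.7 / 380 = 3.9% of true TEAEs with a missing day.
- Visit 13 falls on study Day 395 - 33 + 1 = 363 to 409 - 27 + 1 = 383, so collection often stops before Day 380. I simulated transplant dates uniform over two years, first dose on Day 27 to 33, Visit 13 on Day 395 to 409, and onset uniform from first dose to the earlier of Visit 13 and Day 380. The share lost is 2.4%.
- The earliest onset that can be lost is Day 351 (Day 380 on the 30th of a 31-day month: 380 - 29 = 351).

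**Missing month, late end.** The lag from consent to first dose is 0 to 33 + 14 = 47 days, so consent to Day 380 spans 379 to 379 + 47 = 426 days. Write Y for the consent year. Rule 2 counts Y and Y+1 only.

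| Lag, consent to dose | Day 380 falls in Y+2 for consents from | Share of consent dates, 2014–2015 |
|---|---|---|
| 0 days | 18 December | 3.7% |
| 14 days | 4 December | 7.5% |
| 30 days | 18 November | 11.9% |
| 47 days | 1 November | 16.6% |

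In the example above, let consent be 18 December 2013 (transplant Day -14). An event dated only 2015 is excluded, yet 1 January to 14 February 2015 is study Day 336 to 380, all in the window. With the same simulation and consent uniform from Day -14 to Day +26, 0.4% to 0.5% of true TEAEs with a missing month are lost.

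**Missing day, early end.** Take a first dose on 20 March 2015 and a serious event with onset in March 2015, day unknown, and stop date 10 March 2015. Rule 3 sets onset to 31 March, which is Day 12, and the event is counted. The onset check box in SAP 7.5.1 does not help, because it applies only to events occurring on Day 1. The result conflicts with the window definition in SAP 7.5.1, and with Protocol 7.6.1, which classes adverse events recorded between consent and first dose as medical history.

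**The case against.** The best case for leaving the rules alone has four parts.

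1. **The late-end loss is remote and probably rare.** No onset before Day 351 can be lost through a missing day. That is 351 - 151 = 200 days after the Dose 5 target day in SAP 7.9.3. Onsets close to Visit 13 are fresh when reviewed there, so a missing day is least likely just where the rule fails. The rule also does not depend on treatment arm. This stands and limits the size. It does not remove the contradiction with SAP 7.5.1.

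2. **Nothing disappears from the report.** SAP 7.9.1 keeps the actual partial dates in the listings, and Protocol 7.6.1 lists all adverse events and also summarises serious events reported at any time after dosing starts (the SAP does not repeat that summary). This stands: the loss is from TEAE summaries only.

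3. **Pre-dose events are already handled.** Protocol 7.6.1 sends them to medical history, and SAP 7.5.1 counts an event that continues from before dosing only if it worsens. Protocol 5.5.6 requires serious events to be reported within 24 hours of awareness, so an unknown onset day should be uncommon. The start-after-stop sentence could also be read as covering adverse events, since its paragraph opens by naming both kinds of record; on that reading the March example would be set to 9 March and not counted. This largely stands as to intent. The sentence's position makes the medication-only reading likelier, however, so the text should be made explicit.

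4. **Counting doubtful early events is deliberate caution.** That is reasonable for an event that may have begun after dosing. It gives no reason to count one known to have stopped before dosing.

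A reader might also infer two stronger claims that the documents do not support. The first is that all events in the second year after consent are dropped. Rule 2 counts calendar year Y+1 in full; only Y+2 with the month missing is excluded, and that is wrong only when the window reaches Y+2. The second is that most partly dated pre-dose serious events would be miscounted. The relevant group is those that both resolved before dosing and would be moved past it. The documents give no durations. With assumed exponential durations of mean 3, 7 and 14 days, and the same assumed spread of consent dates, that group is about 49%, 36% and 24% of pre-dose serious events with a missing onset day. The figure is therefore driven by assumption.

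**Conclusion.** The late-end point holds on the text. Rule 3 excludes day-missing events in Day 380's month unless Day 380 is a month end, and rule 2 excludes month-missing events in calendar year Y+2 even when the window reaches that year. With even onset, about 2.4% and 0.4% to 0.5% of the respective true TEAEs are lost. These percentages assume evenly spread transplant, consent and onset dates, and they apply only to events with partial dates. The documents do not say how many such events to expect, so no count can be given.

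The early-end point holds in a narrow form: no stop-date check is clearly stated for adverse events, so a resolved pre-dose serious event with a missing onset day could be counted against the evident intent of Protocol 7.6.1 and SAP 7.5.1.

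This is a minor correction. The efficacy analyses are unaffected, and nothing here suggests that the safety conclusions would change.

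**What to change.** Replace the three adverse-event rules in SAP 7.9.1 with:

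> An AE with a partial onset date is treatment-emergent if its possible onset range (the stated month, or the stated year when the month is missing) overlaps Day 1 to Day 380. An AE with a missing year or wholly missing onset date is treatment-emergent. In all cases, an AE with a known stop date before Day 1 is not treatment-emergent.

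The first sentence repairs both late-end errors and keeps the caution at the start of the window. The second keeps rule 1's treatment of a missing year and states it for a wholly missing date. The third supplies the stop-date check.

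The cost is a few lines of text and code. The downside is that a few events that truly began after Day 380 may be counted. SAP section 1 has the plan signed before hard lock and unblinding, so the change should be made before then, without knowledge of treatment.

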7.9.2 Outliers

All values will be included in the analyses.

7.9.3 Visit Windows

The screening visit, all dosing visits, post dosing visits, Month 8 and End of Study visits for analyses will be based on dates relative to date of first study drug injection (Day 1) according to the table below:

CRF Visit	Target day	Range	Analysis visit
1	-43 to 1	-43 to 1	Screening
2	1	1 to 1	Dose 1
3	15	12-18	Post Dose 1
4	31	26-36	Dose 2
5	45	42-48	Post Dose 2
6	61	56-66	Dose 3
7	75	72-78	Post Dose 3
8	91	86-96	Dose 4
9	105	102-108	Post Dose 4
10	151	146-156	Dose 5
11	165	162-168	Post Dose 5
12	241	231-251	Month 8
13	366	352-380	End of Study

If a dose is missed, the subject should continue on the same schedule of study drug injections and the same schedule of assessments except for the 14 days after dose visit for the missed dose; clinical labs for hematology, biochemistry and hepatic profile should not be collected. Scheduled Immunogenicity Labs (Visit 5 & 9) must still be collected.

If there is ambiguity about numbering of a visit, then visit number will be assigned so that no two visits are assigned the same visit number, and (1) the value which assessment day is the closest to the defined target day within these windows is used; (2) if two values are equally close, the later is used in the analysis; (3) if the assessment should be performed before each dosing then the value collected last before dosing will be used; (4) if the assessment should be performed on the same day as a dosing day then the assessments closest to the day of the injection should be used.

Analyses will not exclude subject data due to the subject's failure to comply with the visit schedule.

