famciclovir should not exceed the following doses following transplant (Day 0) through one year post first Study Drug injection (Day 395/Visit 13).

Aciclovir: 1600 mg orally (total daily dose), or 500 mg/m²/dose IV (total daily dose)

Valaciclovir: 1000 mg orally (total daily dose)

Famciclovir: 500 mg orally (total daily dose)

These doses may be exceeded if necessary to treat active infections.

Pneumocystis jiroveci Pneumonia Prophylaxis

Pneumocystis jiroveci pneumonia prophylaxis must be initiated for all study participants according to the site's standard practice for kidney transplant recipients and applied uniformly to all enrolled subjects. Dose may be adjusted or therapy interrupted for renal dysfunction, adverse events related to the administration of the therapy or for other clinically indicated reasons. If there is no prophylactic *Pneumocystis* protocol, the investigator must decide on appropriate *Pneumocystis jiroveci* pneumonia prophylaxis.

Prohibited Concomitant Medications (Drugs and Therapies):

- Investigational research products through completion of Day 395 visit (Visit 13).
- Planned Alemtuzumab and, anti-CD20 antibodies (including rituximab), eculizumab or bortezomib are not allowed from the Day of Randomization through the Primary Study Period (Day 395). These treatments may be given after the Day of Randomization if clinically indicated.
- Prophylactic use of CMV immunoglobulin.
- Live attenuated vaccines within one month (30 days) prior to each dose of Study Drug.
- Subunit or killed vaccines within 14 days before any Study Drug injection.
- Anticoagulants, within 5 half-lives of Study Drug administration, including but not limited to vitamin K antagonists, heparin or its derivatives, low molecular weight heparin, factor X inhibitors, or thrombin inhibitors. Low dose anticoagulants that are used for prevention of deep vein thrombosis and antiplatelet agents are allowed.

Duration of Treatment:

Subjects will receive either 5 doses of ASP0113 or 5 doses of placebo on Days 30 ±3, 60 ±5, 90 ±5, 120 ±5, and 180 ±5 in relation to the day of transplant.

Discontinuation Criteria:

Study and Treatment Discontinuation

Subjects will be withdrawn from investigational study treatment and all follow up assessments and will only be followed for mortality through public records if the following occurs:

- Withdrawal of consent by the subject.

Treatment Only Discontinuation

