1. Baseline is date of first dose (Visit 2). The day of transplant is Day 0 and all visit days are relative to Day 0 with the exception of the injection safety follow up visits which are relative to each dose. A visit window is allowed for each visit.
2. Screening and baseline visits may take place on the same day if all clinical labs as measured by the local laboratory meet inclusion and exclusion criteria.

Long-term Follow-up Period: Primary Study Period Completion through Long-term Follow-up Completion (Day 395/Visit 13 through 5.5 years post first Study Drug injection)

Long-term Follow-up Contact*	Long-term Follow-up Contact*	Long-term Follow-up Contact*	Long-term Follow-up Contact*	Long-term Follow-up Contact*
1.5 Years Post first Study Drug injection	2.5 Years Post first Study Drug injection	3.5 Years Post first Study Drug injection	4.5 Years Post first Study Drug injection	5.5 Years Post first Study Drug injection

- * Subjects will be contacted by telephone at 6 months after Day 395, then annually for the next 4 years, to evaluate for long-term safety related to the DNA vaccine. Items to be assessed by questionnaire and available patient records are mortality, development of any new malignancies, development of infection requiring hospitalization or resulting in death, graft survival, creatinine and erythema and induration at the injection site. Subjects that discontinue treatment early will be followed per the same schedule.

Table 1: Schedule of Assessments

	Screening ¹	Baseline Randomization and Dose 1		Dose 2		Dose 3		Day 100	Dose 4		Dose 5		Study Completion/ Early Termination ²³	
Visit Number	1	2	3*	4	5	6	7*		8	9	10	11*	12	13
Day (From Transplant for dosing visits or prior dose)	-14 through +30 Day of Transplant = Day 0 ²	30	14 days after Dose 1 ²⁵	60	14 days after Dose 2 ²⁵	90	14 days after Dose 3 ²⁵		120	14 days after Dose 4 ²⁵	180	14 days after Dose 5 ²⁵	270	395
Visit Window (days)		+/-3	+/- 3	+/- 5	+/- 3	+/- 5	+/- 3		+/- 5	+/- 3	+/-5	+/- 3	+/- 10	+14
Month		1		2		3			4		6		9	13
Valganciclovir/Ganciclovir ³	By Day 10 Post Transplant →													
Informed Consent ⁴	X													
Subject Number Assignment ⁵	X													
Inclusion/Exclusion Assessment	X	X ^P												
EQ-5D, KTQ, SF-12 ⁶		X ^P		X ^P		X ^P			X ^P		X ^P			X
Medical History & Demographics ⁷	X													
Clinical Evaluation (Physical Exam & Vitals) ⁸	X	X ^P		X ^P		X ^P			X ^P		X ^P		X	X

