Concomitant Medication Review (including immunosuppressants) ⁹	X	X ^P		X ^P	X	X ^P			X ^P	X	X ^P		X	X
Health Economic Assessment (HEA)	X	X ^P		X ^P		X ^P			X ^P		X ^P		X	X
Clinical Laboratories ¹⁰	X	X ^P	X	X ^P	X	X ^P	X		X ^P	X	X ^P	X		X
Urinalysis, with Microscopic Evaluation	X	X ^P	X	X ^P	X	X ^P	X		X ^P	X	X ^P	X		X
Urine:Protein Creatinine Ratio	X	X ^P	X	X ^P	X	X ^P	X		X ^P	X	X ^P	X		X
Pregnancy Test (females) ¹¹	X	X ^P		X ^P		X ^P			X ^P		X ^P		X	X
CMV Serologies ¹²	X													
Adverse Event and SAE Review ¹³	X	X ^P		X ^P	X	X ^P			X ^P	X	X ^P		X	X
Transplant Information ^{14, 15}		X												
Randomization ¹		X ^P												
CMV Plasma Viral Load Testing (see Table 1a) ^{16, 17, 24}									Every 2 Weeks →			Monthly →		
CMV Genotypic Resistance Testing, when applicable ^{18, 24}			→											
Immunology Lab ^{19, 24}		X ^P			X	X ^P				X	X ^P			X
Pharmacogenomics (PGx) – (Optional) ^{20, 24}		X ^P												
Study Drug injection ²¹		X		X		X			X		X			
Local & Systemic Reactogenicity Assessment ²²		X		X		X			X		X			
Patient and Graft Survival														X

P = procedure should be completed prior to dosing * = Visit procedures may be performed by Home Health Care (HHC)

Table 1a: Plasma Viral Load Schedule

	Every Other Week							Monthly							
	Day 100*	Day 114*	Day 128*	Day 142*	Day 156*	Day 170*	Day 184	Day 198*	Day 230*	Day 260	Day 290*	Day 320*	Day 350*	Day 380*	Day 395
CMV Visit Window (days)	+/-3	+/-3	+/-3	+/-3	+/-3	+/-3	+/-5	+/-5	+/-5	+/-5	+/-5	+/-5	+/-5	+/-5	+14/-5
CMV Window							Day 179-189	Day 193-203		Day 255-267					
Overlap with Regular Visit†							Days 179-185	Days 191-197		Days 260-267					Days 395-409
May draw with Visit:	Visit 7*						Visit 10	Visit 11*		Visit 12					Visit 13
CMV Plasma Viral Load Testing ^{16, 17, 24}	X	X	X	X	X	X	X ^p	X	X	X	X	X	X	X	X

* = Visit procedures may be performed by Home Health Care (HHC). Viral load blood draws may be combined with Visits 10, 11 12 & 13 at the investigator site when they are scheduled to coincide within each visit’s windows .

† Days in Study Schedule when CMV and Regular Visit can be performed together per Protocol. The overlap used assumes the visits are done exactly on the specified visit day from Transplant. If +/- window is used for a dosing visit, the corresponding follow up visit should take place within the 14 days +/-3 from the date of the Study Drug dose. Visits 10 & 11 must be at least 7 days apart.

Tables 1 and 2 Footnotes:

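### SAP 7.9.3 keeps the protocol's ±5 and ±3 day half-widths but counts from the first injection, so many compliant visits miss their analysis window and no rule clearly assigns them

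*SAP*

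**What the plan says.** SAP 7.9.3 covers the screening, dosing, post-dose, Month 8 and End of Study visits: "visits for analyses will be based on dates relative to date of first study drug injection (Day 1) according to the table below". Doses 2-5 have targets of Days 31, 61, 91 and 151, each ±5. Post Doses 2-5 have targets of Days 45, 75, 105 and 165, each ±3; the range for CRF Visit 5, for example, is given as "42-48 Post Dose 2".

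The protocol uses other starting points. Under Duration of Treatment in the Synopsis, injections are given "on Days 30 ±3, 60 ±5, 90 ±5, 120 ±5, and 180 ±5 in relation to the day of transplant". The note to the flow chart says that "all visit days are relative to Day 0 with the exception of the injection safety follow up visits which are relative to each dose". The footnote to Table 1a adds that, where a dose is given off its nominal day, "the corresponding follow up visit should take place within the 14 days +/-3 from the date of the Study Drug dose".

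SAP 7.9.3 has four selection rules for cases where visit numbering is ambiguous. Under rule (1), "the value which assessment day is the closest to the defined target day within these windows is used". Rules (3) and (4) concern pre-dose values and values due on a dosing day. The section closes with: "Analyses will not exclude subject data due to the subject's failure to comply with the visit schedule".

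SAP 7.1 ends the data for the primary study period at Day 380 (365 + 14 + 1). Protocol Table 1a allows Visit 13 on Days 395-409 from transplant.

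**The concern.** The SAP moved every visit onto one clock but left the half-widths unchanged. On that clock, a later dose carries its own permitted deviation and that of Dose 1. A post-dose visit carries both of these and its own ±3. The windows make room for only one of them. A subject who follows the protocol exactly can therefore have a visit on a day that belongs to no analysis visit, or to a different one.

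By-visit results are at stake. SAP 7.4.4 compares the arms on immunogenicity at each measurement visit. SAP 6.1.4 lists Post Dose 2 and Post Dose 4 among those time points, two of the five after baseline. The laboratory summaries in SAP 7.5.3 refer to 7.9.3 directly. If out-of-window values are dropped, these results rest on fewer subjects than were sampled. If they are kept, someone has to choose an assignment rule that the SAP does not contain.

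**Working it through.** **1. Reproduce the SAP targets.** Target = protocol day − 30 + 1, plus 14 for a post-dose visit.
- Doses 2-5 (Days 60, 90, 120, 180): 31, 61, 91, 151.
- Post Doses 2-5: 45, 75, 105, 165.
- Visit 12 (Day 270): 241. Visit 13 (Day 395): 366.

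All agree with the SAP table. The dose and post-dose half-widths are the protocol's own.

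**2. Permitted deviations.** Let e1 be the Dose 1 deviation (−3 to +3, 7 values), e2 that of a later dose (−5 to +5, 11 values) and e3 that of the post-dose visit (−3 to +3, 7 values). In days from first injection:
- dose visit = target + e2 − e1, window ±5;
- post-dose visit = target + e2 − e1 + e3, window ±3.

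A compliant post-dose visit can thus be 3 + 5 + 3 = 11 days from target. For Post Dose 2 that is Days 34-56. Post Dose 1 is unaffected, because the first injection is its proper starting point.

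**3. One example.** Dose 1 is on Day 32, Dose 2 on Day 57 and the follow-up on Day 70 (13 days later), all compliant. The follow-up is on study day 70 − 32 + 1 = 39, between the Dose 2 window (26-36) and the Post Dose 2 window (42-48).

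**4. Dose visits, all allowed days equally likely.** There are 7 × 11 = 77 combinations. A visit is outside when |e2 − e1| > 5, which happens for 1, 2 and 3 values of e2 when |e1| is 1, 2 and 3. Total: 2 × (1 + 2 + 3) = 12, and 12/77 = 15.6%. All 12 fall in no window.

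**5. Post-dose visits, same assumption.** There are 7 × 11 × 7 = 539 combinations. Put k = e3 − e1, which arises in 7 − |k| ways. The number of e2 values that keep the visit inside ±3 is 7 for |k| ≤ 2, then 6, 5, 4 and 3 for |k| = 3, 4, 5 and 6. Inside: 7×7 + 2 × (6×7 + 5×7 + 4×6 + 3×5 + 2×4 + 1×3) = 49 + 254 = 303. Outside: 539 − 303 = 236, or 43.8%.

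Of those 236 for Post Dose 2, 10 land in the Dose 2 window and 1 in the Dose 3 window. That leaves 225/539 = 41.7% in no window; Post Dose 3 gives the same. For Post Doses 4 and 5 it is 226/539 = 41.9%.

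**6. Other timing assumptions** (share outside own window):

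| Timing within allowed days | Dose 2-5 | Post-dose 2-5 |
|---|---|---|
| Equally likely | 15.6% | 43.8% |
| Triangular, peaked on target | 5.2% | 29.6% |
| Normal, SD = half-width/2 | 3.6% | 25.5% |
| Normal, SD = half-width/3 | 0.4% | 10.5% |
| All at window edges | 50% | 75% |

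**7. Later visits, equally likely days.** For Visit 12 (±10), 12 of 7 × 21 = 147 combinations are outside (8.2%). For Visit 13 (0 to +14), the latest study day is 409 − 27 + 1 = 383. The days beyond 380 are Dose 1 on Day 27 with Visit 13 on Days 407-409, Day 28 with 408-409, and Day 29 with 409: 6 of 7 × 15 = 105 (5.7%).

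**The case against.** The strongest reply is that the SAP need not be read as discarding anything. Its table has a CRF Visit column, and the selection rules apply only when numbering is ambiguous; a sample recorded under CRF Visit 5 may not be. Rules (3) and (4) tie pre-dose and dosing-day values to the injection. The closing sentence keeps data from subjects who miss the schedule, and SAP 7.9.2 keeps all values. It would be odd to keep non-compliant visits and drop compliant ones.

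This stands in part. Assignment by CRF visit is a possible reading, and rules (3) and (4) may rescue many dosing-visit values. So certain data loss, which a reader might infer, is not established. But the governing sentence assigns visits by date, rule (1) works only inside the windows, rules (3) and (4) do not reach post-dose visits, and the closing sentence does not say which visit a stray value joins. If CRF visits were meant to decide, the ranges would have little function.

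The size can also be over-read. The 44% is neither a maximum nor the share in no window: it is the share outside the visit's own window under one assumed distribution. A reader might also infer an immunogenicity comparison of about 39 per arm (70 × 0.562). That needs equal likelihood, strict exclusion and a sample from all 70, although T-cell samples are not collected at low lymphocyte counts (SAP 6.1.4). Triangular timing would leave about 49 (70 × 0.704).

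Finally, the first-injection clock still works when a dose is missed, whereas a clock based on the actual dose does not. That is a fair point, and the fix has to allow for it.

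**Conclusion.** The mismatch follows from the documents' own numbers and does not depend on any assumption about timing: the windows cannot contain all compliant dose 2-5 and post-dose 2-5 visits, and no rule clearly assigns the rest. The size does depend on timing, which the documents do not give. With equally likely, independent days, about 44% of post-dose 2-5 visits are outside their own window (about 42% in no window, about 2% in a dosing-visit window) and about 16% of dose 2-5 visits are in no window. Triangular timing gives about 30% and 5% outside their own window. Tight clustering still misplaces about one post-dose visit in ten.

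The effect is limited to by-visit results, chiefly immunogenicity at Post Dose 2 and Post Dose 4 and the laboratory summaries. Vital signs are not scheduled at post-dose visits, reactogenicity is tied to each injection, the liver categories use all post-baseline values through Day 380, and the primary endpoint uses all central viral loads from the first injection through Day 380. None of these depends on the post-dose windows.

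A reader might infer from the late Visit 13 cases that the Day 380 cutoff should move for everything. The documents do not support that. Only 6 of 105 combinations are affected, and the same cutoff bounds the primary endpoint, censoring and treatment-emergent adverse events, in a trial whose futility looks have already been conducted (SAP 7.8).

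**What to change.** Amend SAP 7.9.3 before unblinding.

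- Assign dose visits by the actual dose record.
- Assign post-dose visits by days from that dose: 14 ±3, widened so that no gaps remain.
- When the dose was missed, use the recorded CRF visit. This fallback is needed because Visit 5 and Visit 9 immunogenicity samples are still collected after a missed dose (SAP 7.9.3; Protocol 5.1.2).
- Alternatively, state that the recorded CRF visit is used whenever it was protocol-compliant. That would also cover Visit 12.
- For by-visit summaries only, extend the End of Study window to Day 383, with an explicit exception to the data limit in SAP 7.1. Leave Day 380 unchanged for the primary endpoint, censoring and treatment-emergent adverse events.

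With dose visits taken from the dose record and post-dose visits windowed from the actual dose, no compliant dose 2-5 or post-dose 2-5 visit falls outside its own window. The cost is a small SAP edit and some programming, using dates already collected.
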